13.0 Study Timeline (optional)

	Pre-Screening	Visit 1	Visit 2	Visit 3	Six week Follow up
Estimated time requirement of visit					
Data Collection					
Study Procedure 1					
Study Procedure 2					
Study Procedure 3					
Phone Call Questionnaire					

14.0 ClinicalTrials.gov Information

Directions: If this study has been registered on ClinicalTrials.gov, provide the ClinicalTrials.gov identifier and the investigator/sponsor responsible for registering. If this study has not been registered on ClinicalTrials.gov, provide the rationale as to why and if/when it will be. If it does not meet the requirement for being registered on ClinicalTrials.gov, please state that.

This study has been registered on ClinicalTrials.gov. This entry was transferred to Case Western, NCT05292248

15.0 List of Data to be Collected

1. *Indicate what identifiers you will collect*

- Name
- Address (e.g., Zip code, other geographical designation, etc.)
- Dates related to an individual (e.g., Date of admission, birth, surgery, etc.)
- Telephone number
- Fax number
- Email address
- Social security number
- Medical record number

- Health plan beneficiary number
- Account number
- Certificate/license number
- Any vehicle or other device serial
- Device identifiers or serial numbers
- Web URL
- Internet protocol (IP) address
- Finger or voice prints (*includes audio recordings*)
- Photographic images (*includes video recordings*)
- Other: Any characteristic that would uniquely identify the individual
If other, please explain: [Click here to enter text.](#)

2. List all other data to be collected for the research study. Attach all data collection tools on the Local Site Documents page of the SpartaIRB smart form (Other Attachments).
Baseline, Follow Up 1, and Follow Up 2 Survey; Daily spending surveys; Qualitative interviews; Intervention fidelity, including CONFIDENCE session recordings;
Characteristics of study participants and non-study participants (Eventbrite registration)

16.0 Online Data Collection

- We will not collect data through an online platform.

1. List the online platform to be used. The preferred platforms are REDCap and Qualtrics, as these provide good data security and have options for collecting data without individually identifiable information.
All survey data will be collected through REDCap. Qualitative interview data will be collected on an institutional Zoom account and recorded. Eventbrite data will also be downloaded on registrants, regardless of study participation

2. If your intent is to collect the data without identifiers linked to an individual (including IP addresses), describe how you will ensure that no identifiable information will be associated with the data.

- Qualtrics: enable Anonymize Responses setting (removes IP addresses and location data)
- REDCap: use of the Public Survey Link
- REDCap: use of a Participant List without a Participant Identifier field
(Note: this does maintain a connection between the data and the individual, but it is only accessible to REDCap support personnel and not the researchers. Data collected in this manner should not be referred to as anonymous, but rather as data that is deidentified to the researchers).
- Other: Study data will be collected in two separate REDCap projects where participants will have separate IDs for eligibility and research data. These will be connected by a study key stored on an encrypted university Box folder.. The first REDCap project will be used to determine eligibility and will include participant identifiers required to administer payments and contact participants. The second REDCap project will exclude participant's names but will include email and cell

phone number to administer surveys and reminders. These data will be marked as “identifiers” in REDCap and will be excluded from data downloads when we go to analyze data.

17.0 Data Analysis Plan

Directions: Describe the data analysis plan, including any statistical procedures. If applicable, provide a power analysis, and study/safety endpoints. Directions: Describe the data analysis plan, including any statistical procedures. If applicable, provide a power analysis, and study/safety endpoints

Participant Demographic Characteristics

Participant characteristics, including age, gender, race, ethnicity, educational attainment, income, employment status, kin relationship to recipient, length of time caregiving, hours of caregiving, and whether the care recipient and caregiver live together will be reported using frequencies, percentages, means, and standards of deviation. *Comparison of Study and non-study participants*. Demographic characteristics of study and non-study participants collected from Eventbrite will be compared using t-test and chi-squared bivariate analyses, as well as frequencies and percentages. **Outcome Measures** *Self-Efficacy (primary outcome)*. Self-efficacy is measured using the Caregiver Self-Efficacy Scale. This 8-item scale combines domains of self-efficacy (e.g., managing behavioral symptoms, accessing respite, and controlling upsetting thoughts. It demonstrates high reliability ($\alpha=0.89$) and good test-retest reliability (0.73). Participants rate the extent to which they are “Not confident at all” (1) to “Totally confident” (10). Scores range from 8 (lowest) to 80 (highest).³⁵ *Resourcefulness (primary outcome)*. Resourcefulness is measured using the 19-item learned resourcefulness scale designed for family caregivers ($\alpha=0.81$). This scale has two factors: one focused on help-seeking and another on self-help. Caregivers are asked the frequency at which they use different strategies to manage challenges, and may respond: . Items are added together to create a total score. Scores range from 0 to 24. Permission was received by the scale’s author to use this tool on April 21, 2022.

Psychological Financial Strain (secondary outcome). Our measure for psychological financial strain is derived from multiple scales, which were selected according to relevance to our caregiving population. Items 1 to 11 ask about financial anxiety and is based on the 10-item scale from Shapiro & Burchell (2012).³⁶ Item 1 is modified such that the question asks about feeling overwhelmed instead of bored. We also added an item based on another related to caregiving (i.e., “I find planning for my caregiving expenses to be unpleasant”). Items 12 to 14 are based on those used by Novilitis et al., (2003), and address additional components of financial anxiety than those items introduced by Shapiro (e.g., arguments with others; $\alpha=0.74$).³⁷ Lastly, we included the 1-item question from Shim et al. (2010) that asks about financial worry (“I worry constantly about money”; CFA factor loading was 0.79 for this item).³⁸

Monthly Spending Report (out-of-pocket costs of caregiving, secondary outcome). Our measure for monthly out-of-pocket costs of caregiving is based on the tool used by the AARP Public Policy Institute in their 2016 report on the out-of-pocket costs of caregiving. We will calculate estimated daily costs using both period survey and daily survey. Period surveys (i.e., baseline and the second follow up surveys) ask about spending: in the last month (30 days) and in the last 12 months but not the last month. When a caregiver indicates paying for an item in the last month, they are asked to provide an estimated cost. (We do not ask about cost in the last year given the likelihood the participant will not be able to accurately recall this cost and may forget some expenses.) The costs for yearly/monthly item are those believed to occur irregularly, such as purchase of devices and rent payments. Daily costs are those anticipated to occur regularly, and are asked about on daily surveys, such as groceries and recreation items for the care recipient. To calculate monthly spending, we will multiply daily spending by 6 to approximate 30

days in a month and add all monthly expenses. While the measure is subject to recall bias and fluctuations in spending, it balances 1) the need to efficiently collect data and 2) reduces recall bias by relying on monthly recall alone. Analysis of Baseline and Follow Up Measures We will used two sets of paired t-tests to examine changes in scores between baseline and follow up surveys. If we discover a p-value of <0.05 after running tests, this will indicate there was a statistically significant difference between scores. We will compare scores from baseline until the first follow up survey and from baseline until the second follow up survey. In addition, we will examine mean scores at each time point, as well as the standard of deviation for all summed scores on each scaled. **Handling of Missing Data Missing daily surveys.** If participants miss a survey, we will adjust the monthly formula such that we will multiply according to the number of days for which surveys are completed to reach 30. For example, if a participant completed 4/5 surveys, we will multiply by 7.5 instead of 6. We will exclude participants who miss more than 2 daily surveys from analyses when examining monthly costs. **Missing data on follow up surveys.** Although data from all participants will be reported in sample descriptives, for all analyses using t-tests, we will use a complete case analysis such that participants with any missing data will be removed from the analytic sample. Although this approach risks missing data bias, multiple imputation and maximum likelihood estimation are not feasible to conduct with bivariate analyses. We will conduct bivariate analyses using a "dummy" variable to identify potential differences between those with complete and incomplete data and will also report the extent of missingness using frequencies and percentages.

Satisfaction Surveys Satisfaction surveys, included in the first follow up survey sent to participants, will be used to examine participant satisfaction with the CONFIDENCE intervention. Participants will be asked about the program's relevance to their care situation, quality of information presented, satisfaction delivery, and enjoyment of the program overall. Each question is asked as a statement to which participants can indicate the extent to which they agree on a 5-point Likert scale. To analyze scale items, we will provide a percentage of each response (e.g., 80% of caregivers "Agreed" or "Strongly Agreed" with this statement).

Fidelity Reports Fidelity reports will be evaluated using total scores averaged across all CONFIDENCE Lessons observed. We will be report these in aggregate and separated by facilitator and observer reports. We will divide reports by scores for adherence and quality. Scores will be reported using a percentage, as prior reports indicate 80% or more on fidelity scores indicates acceptable levels of fidelity. In addition—to examine variability in scores—we will also report this information using means and standards of deviation. **Qualitative Interviews**

Qualitative interviews will be transcribed verbatim and identifying information removed. For interviews conducted in Spanish, interviews will be translated by a native speaker. To conduct our thematic analysis, at least two members of the research team will read at least 2 transcripts and will decide on a preliminary codebook.³⁹ The codebook will be applied to an interview and refined further prior to applying codes to the remaining interviews. At least two coders will analyze each transcript independently and will meet to compare codes and discuss differences in coding until agreements met. A second round of coding will be conducted to integrate new codes added during coding. **Statistical Power and Same Size** Our goal is to recruit at least N=60 of these caregivers into a research study to test preliminary efficacy. This N supports our ability to detect a small to moderate effect size in a two-tailed t-test at alpha=0.05 at 80% power.

Sub-study (8/2023 Modification): To analyze data in the sub-study, we will conduct a content analysis of the types of expenditures covered by participants, wherein we will report the frequency with which each expense was described. At least two coders will independently review codes in NVivo 12; when there are disagreements over coding, an agreement will be reached through discussion. Data on out-of-pocket spending will be analyzed using frequencies

and percentages to describe each type of cost, as well as means and standards of deviation to describe estimated expenditures for each cost. Survey data will be analyzed in Stata 17. (Note that data collection for surveys is ongoing, such that the total sample is not yet available.)

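### Does a stated range of 0 to 24 for the summed 19-item resourcefulness scale require a change to the analysis plan?

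*Combined protocol and SAP*

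**What the plan says.** In section 17.0, under Outcome Measures, the plan describes the instrument thus: "Resourcefulness is measured using the 19-item learned resourcefulness scale designed for family caregivers". It adds "This scale has two factors: one focused on help-seeking and another on self-help" and, on the response format, "Caregivers are asked the frequency at which they use different strategies to manage challenges". The response options that should follow are blank in the available text. On scoring it says "Items are added together to create a total score. Scores range from 0 to 24".

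For the other outcome labelled primary in that section, self-efficacy, the plan says "This 8-item scale combines domains of self-efficacy". Each item is rated from 1 to 10, and the stated total runs from 8 to 80.

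The scores are used in two ways. The tests are given as "We will used two sets of paired t-tests to examine changes in scores between baseline and follow up surveys", and the descriptive summary as "we will examine mean scores at each time point, as well as the standard of deviation for all summed scores on each scaled". The sample-size paragraph justifies N=60 by a small to moderate effect size at two-sided alpha 0.05 and 80% power.

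**The concern.** Adding 19 items that share one integer response scale cannot give a total running from 0 to 24. Either the item count, the set of items summed or the range appears to be wrong, and the plan does not show which.

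This matters on its face because section 17.0 labels resourcefulness primary and the central hypothesis in section 2.0 names it. Two things could be at stake. A reader could misjudge reported means and changes if they are set against the wrong maximum. And if 0 to 24 belonged to a subset of items, the plan would not say which items make up the endpoint.

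**Working it through.** **Inputs (all from section 17.0).** Resourcefulness: 19 items, plain sum, stated range 0 to 24. Self-efficacy: 8 items coded 1 to 10, stated range 8 to 80. Planned N = 60. The resourcefulness item codes are not available.

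**Formula.** For n items on one common integer scale with codes from L to H, the minimum is n × L, the maximum is n × H and the width is n × (H − L). Shifting the codes or reverse-keying items leaves the width unchanged.

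**Control: self-efficacy.** Minimum 8 × 1 = 8; maximum 8 × 10 = 80. The stated range is reproduced, so the plan uses range in the ordinary sum-score sense.

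**Resourcefulness.** The width must be 19 × (H − L). The stated width is 24 − 0 = 24 = 1 × 19 + 5, which is not a multiple of 19. The stated range is not reproduced. The possible ranges on a common scale are:

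| Response options | Codes from 0 | Codes from 1 |
|---|---|---|
| 2 | 0 to 19 | 19 to 38 |
| 3 | 0 to 38 | 19 to 57 |
| 4 | 0 to 57 | 19 to 76 |
| 5 | 0 to 76 | 19 to 95 |

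**What would give 0 to 24.** On a common scale from 0, the item count must divide 24: for example 24 items coded 0–1, 12 coded 0–2, 8 coded 0–3 or 6 coded 0–4. With all 19 items, a mixed format is needed: 14 × 1 + 5 × 2 = 24, or 18 × 1 + 1 × 6 = 24. The plan describes neither a subset nor a mixed format.

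**Does the range enter the analysis?**

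- *Paired t-test.* t = mean(d) / (SD(d) / √n), where d is follow-up minus baseline. The theoretical maximum does not appear. If every total were rescaled as a + b × score with b > 0, mean(d) and SD(d) would both be multiplied by b, and t and p would not change.
- *Sample size.* For a paired t-test with n = 60, two-sided alpha 0.05 and 80% power, the detectable effect is 0.368 standard deviations of the change. That agrees with the plan's small to moderate description. It is in SD units and does not depend on the range.
- *Means and standard deviations.* They are computed from observed totals, not from the printed limits.
- *Decision rules.* Section 17.0 sets no cut-off, responder definition, minimal important change, or floor or ceiling rule on this score. The complete-case rule there, the removal rule in section 23.0 and the survey checks in section 28.0 do not refer to the range.

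**The case for a change.** The strongest case for a change is this. The plan calls the outcome primary, the arithmetic fails under every common integer coding, and the self-efficacy line in the same section shows that the authors meant range in the usual sense. The blank response options do not rescue the figure, because no common coding of 19 items gives a width of 24. If a subset or mixed format is the explanation, the endpoint is under-described, and the quoted alpha of 0.81, given for the 19-item scale, would not be documented for a subset. Checking one line against the questionnaire would cost almost nothing.

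The arithmetic stands, and so does the observation that no other section resolves the mismatch. The rest carries less weight:

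- The contradiction depends on all items sharing one format. That is the natural reading, but the text that would settle it is missing and may have been lost in reading the PDF.
- The undefined-endpoint argument is hypothetical. The plan says the items are added into a total and gives no sign that only some are scored. The two-factor remark does not supply a subset, since the range is attached to the total score and the items per factor are not given.
- The appeal to primary status is weaker than it looks, because section 12.0, under Survey Administration, gives that standing to average daily spending.
- A low cost is not a gain. A correction would alter one descriptive figure, and the documents do not allow the right figure to be named.

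**Conclusion.** The item count and the stated range do not agree if the 19 items share one integer response scale. The stated maximum is then either at least 5 points too high (24 − 19 = 5) or, if items have three or more options coded from 0, at least 14 points too low (38 − 24 = 14). It is a descriptive slip, or a description that the available text leaves incomplete.

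It does not call for a change to the plan. The instruction that determines the data is to add the items, and that is clear. The effect on the planned tests, the sample size and the conclusions is nil on everything the documents show. Whoever reports the scores will have the questionnaire and can quote its range beside the means and standard deviations.

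This rests on two assumptions: that all 19 items are summed, as the plan's wording implies, and that no threshold on the score is applied outside these documents. If only a subset were scored, the score itself would differ, but nothing in the plan points that way.

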2.0 Objectives

Directions: Describe the purpose, specific aims or objectives. Be sure to also include the hypothesis being tested. The overall objective of this project is to test the preliminary efficacy that participation in the CONFIDENCE intervention improves caregiver learned resourcefulness and self-efficacy, as well as distal outcomes including monthly out-of-pocket costs of caregiving and financial anxiety/worry. The central hypothesis is that caregivers who participate in the CONFIDENCE intervention will report higher levels of learned resourcefulness and self-efficacy following participation in the CONFIDENCE intervention in follow up surveys as compared to levels found at baseline.

A secondary objective of this research (sub-study, modification submitted 8/2023) is to characterize out-of-pocket spending by Latino family caregivers to persons living with dementia on care-related expenses.

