timeline for the Baseline survey. If so, we will continue to allow them to participate in the study without complete they daily spending surveys, so long as the Baseline survey is completed prior to the first intervention session. This will enable us to still collect data about outcomes besides out-of-pocket costs of care. A follow up survey will be sent immediately after the participant completes the intervention (within 48 hours) and will also ask about participant satisfaction with CONFIDENCE. A second follow up survey will be sent 8 weeks after the intervention is complete. After the participant completes the second follow up survey, they will receive a second set of daily spending diaries administered in the same way as the first set of diaries. Follow up surveys are expected to take approximately 20 to 30 minutes to complete. Participants will receive up to 5 reminders to complete the baseline and follow up surveys, include 3 emails prompts and up to 2 phone calls. Participants will receive a text message reminder, if they choose, reminding them to complete daily spending surveys each night. **Qualitative interviews.** Up to 15 participants will also be asked to participate in a one-on-one qualitative, in-depth, semi-structured interview as well about their experiences with the program, which is expected to take approximately 45 minutes depending on how much the participant would like to share. Selection of interview participants will be based on purposeful sampling, with the goal of recruiting a qualitative sample that includes a range of care experiences according to participant gender, age, employment status, and kin relationship to the person to whom care is provided. Interviews will be completed over Zoom and recorded and later transcribed. Participants will be invited to complete this interview after completing the CONFIDENCE program. If the participant agrees to participate, they will receive a study information sheet by email prior to attending the interview and will review this information sheet before completing the interview. **Payment for surveys and qualitative interviews.** Amazon gift cards will be sent to participants by email for each study activity (surveys and interviews). We will pay participants for the baseline and first set of diaries surveys within a week of when the first set of diaries are due. A second payment will be administered within a week of the first follow up survey being completed. The remaining payments will be sent the week of the second set of diary surveys are due/completed. Payment for interviews will be sent within 1 week of completing the interview. Participants may earn up to \$125 for participating, or \$150 if they complete the qualitative interview. Participants may earn \$25 for each study activity. **Fidelity.** Fidelity will be monitored by an observer (PI or research assistant) and the CONFIDENCE program facilitators. We will monitor one randomly selected CONFIDENCE lesson for each cohort. The selected lesson will be based on Stata's random number generator. The facilitators will know in advance of each lesson if selected for monitoring so they may record lesson. The facilitator will be sent a survey within 24 hours of completing selected sessions to self-monitor delivery. Fidelity surveys will be sent by the PI using REDCap. Session recordings will be stored in the USC CONFIDENCE Office 365 Shared folder and deleted once fidelity forms are completed. The research assistant or PI will watch the recording and complete the fidelity survey within 2 weeks of the lesson taking place. **Attendance.** The USC facilitator will monitor attendance at CONFIDENCE sessions and will store this information in a shared Office 365 folder. The study team will extract information about attendance from study participants from Excel files where attendance is marked and enter it into REDCap for study participants. **Comparison of registrant demographics and study participants.** In addition to data collected from surveys, we will compare the demographic characteristics of individuals who register for CONFIDENCE to participate in the educational program alone with those of study participants. This information can help to inform future recruitment methods by helping the study team understand differences in the characteristics of those who choose to participate in research and those who do not. As a part of their funder's requirements, USC must report on demographic characteristics of program participants to the sponsor. They currently collect this information using the Eventbrite registration page. The Case Western investigators will already have access to the Eventbrite form information to identify participants who are interested in participating in the research study. To compare the characteristics of study participants to non-study participants, we will download Excel files directly from Eventbrite onto an encrypted university Box folder, and add an indicator variable to indicate whether or not individual registrants were in the research study. Once this occurs, all identifiable information will be removed from Excel files and the file will be saved so we can conduct analyses and compare characteristics of study and non-study participants. **Participant safety and monitoring adverse events.** *Adverse events.* Adverse events and protocol deviations will be recorded on an adverse event form by the study team member (PI or RA) who first observes this event. Adverse events pertaining to participant safety and confidentiality will be promptly reported by the PI by phone. Where the RA or PI suspects risk of harm to self or others, this will be reported to USC PI [name], who is a licensed clinical psychologist with extensive experience working with caregivers. [name] is the director of the USC Family Caregiver Support Program where CONFIDENCE is being administered. She will reach out to the participant by phone to conduct further assessment and a safety plan. All protocol deviations and adverse events will be promptly reported to the Institutional Review Board by the PI. Serious adverse events will be reported within 24-hours. **Data and Safety Monitoring.** The PI will complete a Data Safety Monitoring Report every 6 months of the study. The Data Safety Monitoring Report will include the following core elements: a) Progress towards enrollment and participant retention; b) Participant characteristics for enrolled and retained participants (e.g., age, race, ethnicity, gender, aspects of the caregiving situation) according to intervention status; and c) Documentation of adverse events, serious adverse events, and unanticipated problems, as defined below, including resolution of these events and study protocol modifications. This report will not contain any participant identifiers. This report will be shared with the USC PI for review.

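### Two primary scales are each tested at two follow-ups at p<0.05, with no primary time point and no statement of which result or combination supports the central hypothesis.

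*Combined protocol and SAP*

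**What the plan says.** Section 2.0 states the central hypothesis: caregivers "will report higher levels of learned resourcefulness and self-efficacy following participation in the CONFIDENCE intervention in follow up surveys", compared with baseline. It joins the two scales with 'and', and it names no particular follow-up.

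Section 17.0 (Outcome Measures) labels self-efficacy and resourcefulness primary, and psychological financial strain and monthly spending secondary. No time point is attached to either primary label.

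Section 12.0 (Survey Administration) sends the first follow-up within 48 hours of the end of the program. For the later one: "A second follow up survey will be sent 8 weeks after the intervention is complete".

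Section 17.0 (Analysis of Baseline and Follow Up Measures) gives the test: "We will used two sets of paired t-tests to examine changes in scores between baseline and follow up surveys". The comparisons are: "We will compare scores from baseline until the first follow up survey and from baseline until the second follow up survey". The decision rule is: "If we discover a p-value of <0.05 after running tests, this will indicate there was a statistically significant difference between scores". The same section promises means and standard deviations at each time point.

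The power statement in section 17.0 covers one two-tailed t-test at alpha 0.05 with N=60 and 80% power, for an effect described as small to moderate. No order of testing, joint requirement or alpha adjustment appears anywhere.

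**The concern.** A gain present just after the program and a gain still present 8 weeks later are different conclusions. The plan does not say which of them the hypothesis is about, or whether one scale is enough. That choice could therefore be made after the results are known. With four tests each held to 0.05, the chance that at least one is falsely significant exceeds the nominal level. A report of preliminary efficacy could rest on one scale at one time without departing from the written rule. The power statement describes one test, so it does not match a four-test plan with no lead.

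**Working it through.** **Inputs from the documents.** Two primary scales; two comparisons per scale; two-sided 0.05 per test; N=60; 80% power (section 17.0). All figures assume 60 complete pairs. The documents give no correlations, so those below are assumptions.

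**The plan's own figure.** For a paired t-test the detectable standardised change is approximately (1.960 + 0.842)/√60 = 0.362. The exact noncentral-t value is 0.368. This lies between the conventional 0.2 (small) and 0.5 (moderate), so the power statement is sound for one test.

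**Number of primary tests.** 2 scales × 2 follow-ups = 4.

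**Chance of at least one p<0.05 with no true change.** Under independence, 1 − 0.95^4 = 0.185. The four tests share participants, and the two changes on each scale share a baseline, so independence is only a reference case. Simulation used paired t-tests with n=60. Figures from separate runs differ by up to about half a percentage point.

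| Assumed correlation, times / scales | Any p<0.05 | Any false rise |
|---|---|---|
| 0 / 0 (exact) | 18.5% | 9.6% |
| 0.5 / 0.3 | about 17% | about 8% |
| 0.7 / 0.5 | about 15% | about 7.5% |

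The false-rise column counts only results in the hypothesised direction. Under independence it is 1 − 0.975^4 = 0.096, against 0.025 for one test. Over a wider grid (0.3 to 0.9 between times, 0 to 0.7 between scales) the two columns run from about 12% to 18% and from about 6% to 9%.

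**What each repair does to power at N=60 and a standardised change of 0.368.**

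- Both scales must rise at one time, each at 0.05: 0.80 × 0.80 = 0.64 if independent, about 66% to 67% with correlation 0.3 between scales, and about 68% to 69% with 0.5. Restoring 80% needs about 76 to 78 analysed participants.
- Holm over two tests, strictest step 0.05/2 = 0.025: per-test power 71%; detectable change at 80% power 0.407; N=73 to keep 0.368.
- Holm over four tests, strictest step 0.05/4 = 0.0125: per-test power 61%; detectable change 0.443; N=86 to keep 0.368.

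**Is four the full family?** Section 12.0 calls average daily spending the primary outcome of interest, while section 17.0 lists spending as secondary. If it counted as a fifth independent primary test, the two-sided figure would be 1 − 0.95^5 = 0.226.

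**The case against.** The strongest reply is that the plan never adopts an any-one-of-four rule. Section 17.0 says only that p<0.05 marks a significant difference in scores. Section 2.0 joins the scales with 'and', which can be read as requiring both. Both comparisons and the means at each time are to be reported, so an early rise that had faded by 8 weeks would be visible. This stands as far as it goes: a reader might infer that one significant result in four proves the intervention works, and the documents do not say so. They do not say what would be enough either, and that is the gap.

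Second, the tests are two-tailed, so about half of the false positives behind the 18.5% would be falls, which contradict the hypothesis. This also stands. The figure relevant to a favourable claim is the 7% to 10%.

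Third, a reader might suspect that the first follow-up is flattered by goodwill, because it also carries the satisfaction items. The documents say nothing about goodwill, and the point does not depend on it.

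Fourth, this is a single-arm pilot of preliminary efficacy, acceptability and feasibility. Without a comparator, even a well-controlled p-value cannot attribute change to the program. That lowers the stakes, but the plan still tests its hypothesis by p-values and still lacks a lead time point.

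**Conclusion.** The gap is real and of modest consequence. Four primary tests run at 0.05 each, with no lead time point, ordering, joint requirement or adjustment. The chance of at least one false favourable result is about 7% to 10%, roughly three to four times the 2.5% of one test. In either direction it is 18.5% if independent and about 15% to 17% under the two assumed correlation settings. It would be wrong to quote 18.5% as the risk of a false claim of benefit: that figure includes falls and treats the four tests as independent. Nor do the documents establish 8 weeks as the right primary time. Section 2.0 treats spending as a distal outcome, so the fact that the only post-program spending reading is at the later survey does not fix the time for the two scales. The sample-size statement is consistent for a single test and needs restating for whatever rule is chosen.

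**What to change.** In section 17.0:

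1. Name one primary time point for both scales and give the reason. Eight weeks would show retention; the immediate reading is also defensible. Label the other supportive. Do this before follow-up scores are examined; the 8/2023 sub-study text says survey collection was still under way. If it is done later, date the change and disclose it.
2. State the success rule: either both scales must rise at p<0.05 at that time, which needs no alpha split, or Holm is applied across whichever tests may count.
3. Restate power under that rule. At N=60 it is about 64% to 69% for requiring both scales at a change of 0.368. Under Holm, the detectable change at the strictest step is about 0.41 for two tests or 0.44 for four. Allow for losses under the complete-case rule.
4. Reconcile the primary label given to average daily spending in section 12.0 with its secondary label in section 17.0, since this sets the size of the primary family.

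The cost is a few sentences and a revised power statement, with no new data. The downside is lower stated power. A result on one scale or at one time alone becomes supportive, or needs a smaller p-value. If 8 weeks is chosen, dropout may also be somewhat higher at that survey.
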